Specific Aims

In 2013, the United States Preventive Task Force (USPSTF) recommended use of annual low dose CT scans (LDCT) to screen high-risk individuals for lung cancer. This recommendation was based on evidence that detecting and treating early-stage lung cancer would greatly lower the risk of dying from this disease. Unfortunately, lung cancer screening rates in the United States are very low— just 3.3% in 2010 and 3.9% in 2015 (1). **Not yet known** is how to effectively promote and increase lung cancer screening while supporting patients and physicians in making this high stakes decision. There is a critical need to develop and implement effective strategies to engage high risk patients, those who have a substantial history of smoking, in a coordinated program of lung cancer screening which includes shared-decision making.

The **long term goal** of this work is to decrease lung cancer mortality through primary care interventions. Such interventions should leverage the patient-physician relationship and support patients to make informed decisions about lung cancer screening that is aligned with current medical evidence and emphasizes patient values and preferences. In 2017, our research team took an initial step to towards achieving this goal by assessing the feasibility of implementing an informed decision making intervention in a single primary care practice among 54 patients who were eligible for lung cancer screening. The intervention centered the Decision Counseling Program ® (DCP)(2) an online software application that focuses on patient education and preference clarification related to lung cancer screening delivered over the phone by a trained nurse educator. DCP results were given to patients and providers. Use of the DCP intervention was feasible, helped primary care patients clarify their preference related to screening, and participants were likely to undergo LDCT screening. We now propose to **modify and expand the intervention**. We will recruit 100 eligible, current smokers from real world primary care practices to participate in a pilot study, outlined in **Figure 1** comparing to usual care by propensity scoring.

[figure not shown]
Aim 1 Compare low dose CT scan completion in the DCP cohort of current smokers versus usual care, propensity-matched controls at 60 days.

Aim 2 Compare the characteristics of the patients not recruited in the study to the characteristics of those who accepted to enroll

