55-74). There were 297 individuals who were reachable and 54 of these were eligible for LCS according to the USPSTF criteria. We were able to contact a higher proportion of current smokers (47%) than former smokers (30%). Eligibility was higher in current smokers (28%) versus former smokers (11%). Also, of the 54 total eligible, 28 enrolled. Despite these small numbers, we were able to show the DCP participation was associated with LDCT completion at 90 days ($p=0.03$).

Study Design We propose a 1 year project including a **6 month intervention** period. This study will be a cohort with comparison to usual care in other practices in the same health system using propensity-matching methodology. **Study population/eligibility** Inclusion/exclusion criteria will be based on the USPSTF and CMS lung cancer screening guidelines: age 55- 80, with a 30 pack year smoking history, no symptoms consistent with cancer, and no CT scan of the lungs within the last year. Physicians will be given the chance to eliminate participants based on limited life expectancy or prohibitive comorbid conditions. Case finding in our prior work was difficult and recruiting active smokers has a higher yield. Prior work indicated that this pool yielded a higher proportion of truly eligible, reachable individuals. Plus, we want to test the feasibility of a more intense smoking cessation intervention. To address recruitment barriers, we will work with practices and PCPs to promote as a study “conducted with the PCP,” including the physician name or practice name when possible on recruitment materials e.g. written letters and email cosigned by their PCP. To address case finding barriers, we will allow patients to easily opt out of future contact via mail, email or phone. We will work with our advisory panel to explore other methods to enhance recruitment and case-finding such as using the secure EMR portal to screen for LCS eligibility and/or updating smoking history. Finally, we have added \$50 patient incentives per patient for participation.

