Data Acquisition Following approval by the CCHS Institutional Review board, lists of potentially eligible individuals from participating and non-participating practices will be obtained from EMR data. These lists will be automatically entered into a REDCap® for CONSORT tracking. Lists will be organized according to PCP whom will be given 7 working days to review lists and eliminate any patient they feel would not be appropriate for this study. Remaining potentially eligible patients will receive a letter, cosigned by their personal physician which introduces the study and offers the opportunity to easily opt out of further contact. After an opt-out period of 7 working days, patients will be contacted, screened for eligibility and invited to participate. After formal consent, we will collect demographics, socioeconomic variables and smoking history. Baseline data will be collected regarding knowledge, preference and decisional conflict related to lung cancer screening. Standard patient education materials will be sent to patients. The DCP session will be conducted within 30 days of enrollment. A follow up telephone call will occur within 30 days of DCP completion, and will include items to assess patient perception of the process, knowledge about lung cancer screening and decisional conflict (Appendix 3) related to lung cancer screening (10). At 60 days after the decision counseling session, patient charts/electronic medical record data will be audited for the primary outcome, LDCT scan report. Prior work showed the average time from DCP to LDCT was ≤ 60 days. Intermediate (process) outcomes in EMR include lung cancer screening discussion, referral/order for LDCT, or referral to the CCHS LHSP. Eligible patients in the usual care group (in the non-participating clinics) will be identified electronically as stated above and LDCT screening assessed in a 60 day study period from their most recent office visit. Information available in EMR for all patients including controls and individuals who are “unreachable” comprises gender, age, race, ethnicity, insurance status, marital status, smoking status, comorbidities, such as COPD, Heart disease, diabetes, hypertension and zip code (surrogate for socioeconomic status). Information collected from individuals who are reached but ineligible will include all of the above plus smoking status, pack years, and reason for ineligibility. Information collected from individuals who decline participation will include all of the above plus reason for declining participation.

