
Statistical analysis

Aim 1 Compare low dose CT scan completion in the DCP cohort of current smokers versus usual care propensity-matched controls at 60 days. *Hypothesis: Participation in the DCP will be associated increased participation in LDCT, compared with both eligible enrollees who do not participate and with eligible patients in usual care practices.* Demographic and clinical variables of the intervention and control groups will be compared using T-Test, Wilcoxon-Rank sum test and chi-squares. We will conduct a 1-to-1 propensity score matching to compare the proportion of patients who screen between the groups. We will use a logistic regression model to build propensity scores to match patients in the intervention and control groups. We will model the probability of being in the intervention group using all the patients level variables extracted from the medical records as listed above. Whether they are in a participating practice or not will not be included in the model as an independent variable. The nearest neighborhood method without replacement will be used for matching. We will set the caliper width according to the standard deviation for the propensity score. Each control will be assigned a probability score and matched with a patient in the intervention group. In a second step, we will compare the characteristics of the patients and chosen controls to verify that they are very similar. We will use a simple chi-square to compare the percentage of patients in the control and intervention groups who complete the LDCT scan within 60 days.

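### The Aim 1 chi-square ignores practice clustering, although each practice supplies only one matched group; the error and power depend on a practice count and ICC that the plan does not state

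*Combined protocol and SAP*

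**What the plan says.** Study Design describes a cohort with "comparison to usual care in other practices in the same health system using propensity-matching methodology". Data Acquisition puts the controls elsewhere than the DCP patients: "Eligible patients in the usual care group (in the non-participating clinics) will be identified electronically". In the matched comparison, practice is therefore nested within group. (The Aim 1 hypothesis also names eligible enrollees who do not take part, but the matching and the quoted test concern usual-care controls.)

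Under Statistical analysis, Aim 1: "We will conduct a 1-to-1 propensity score matching to compare the proportion of patients who screen between the groups". The propensity model uses patient-level EMR variables, and "Whether they are in a participating practice or not will not be included in the model as an independent variable". The outcome test is then: "We will use a simple chi-square to compare the percentage of patients in the control and intervention groups". No mixed model, GEE, cluster-robust variance or practice-level analysis appears anywhere.

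The power paragraph gives 85% for 40 per group (15% against 45%), expects 150 DCP participants, and calls the power for a 20-point difference ample. Specific Aims gives a smaller target: "We will recruit 100 eligible, current smokers from real world primary care practices to participate in a pilot study". No section states a number of practices, an ICC or a within-pair correlation, and Community Engagement lists practice selection among the topics on which the advisory team will advise.

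**The concern.** Patients of one practice share clinicians, referral routes and habits, so their screening outcomes may be correlated. When each practice contributes to one group only, a positive correlation does not cancel in the between-group difference. It adds to the variance, and the simple chi-square omits that part. The result can be a p-value that is too small, an interval that is too narrow and a power figure that is too favourable.

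The documents give qualitative reasons to expect some correlation. Under Intervention, the steps after counselling are adapted to each practice (this applies to DCP patients). Innovation names physician recommendation as a leading predictor of cancer screening (a general statement). Aim 1 is the primary outcome comparison and is meant to prepare a larger randomised trial, so an overstated result would carry forward.

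**Working it through.** **Plan's own figure.** Two-proportion formula with pooled variance under the null, independent patients, two-sided 5% (the plan does not state alpha). 40 per group, 15% against 45%, gives 84.7% (85.2% by exact enumeration), against the stated 85%. The stated power therefore contains no clustering allowance.

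**Assumptions.** ICC 0.01, 0.02 or 0.05; 5 or 10 DCP practices and 5 to 20 control practices; equal practice sizes; n = 100 (Specific Aims) or 150 (power paragraph) per group. Only the two values of n come from the documents.

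**Type I error of the planned test.** With k practices in a group, m = n/k and the design effect is 1 + (m - 1) x ICC. Let D be the mean of the two groups' design effects. The actual error is 2 x [1 - Phi(1.96/sqrt(D))].

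- 5 v 5 practices, n = 100, ICC 0.05: m = 20, D = 1 + 19 x 0.05 = 1.95, 1.96/1.396 = 1.404, error 16.0%. A beta-binomial simulation of 100,000 runs gave 16.2%.
- 10 v 20 practices, same n and ICC: design effects 1.45 and 1.20, D = 1.325, error 8.9%.

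If matching induces a within-pair correlation r, the variance factor becomes D - r. The value r = 0.12 is an assumption used to show the offset.

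| n per group | r | ICC 0.01 | ICC 0.02 | ICC 0.05 |
|---|---|---|---|---|
| 100 | 0 | 5.8-7.2% | 6.5-9.5% | 8.9-16.0% |
| 100 | 0.12 | 4.4-5.8% | 5.1-8.1% | 7.4-14.7% |
| 150 | 0 | 6.2-8.4% | 7.4-11.9% | 11.1-21.1% |
| 150 | 0.12 | 4.8-7.0% | 6.0-10.5% | 9.7-19.9% |

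In each cell the low end is 10 v 20 practices and the high end 5 v 5. With r = 0.12 the test exceeds 5% only above a break-even ICC of 0.12/mean(m - 1). At n = 100 that is 0.12/19 = 0.006 for 5 v 5 and 0.12/6.5 = 0.018 for 10 v 20.

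Fewer or uneven practices make matters worse. Two practices per group (n = 100, r = 0) give 10.8%, 16.4% and 29.1% at the three ICCs. Uneven sizes (coefficient of variation 0.6, 5 v 5, pairing ignored) gave 8.0%, 11.1% and 19.1% in simulation.

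**Power of a clustered test, 15% against 35%.** A normal reference is not adequate here: with 5 practices per group it rejects about 8.6% under the null. With a t reference, the variance is [p1(1 - p1)D1 + p0(1 - p0)D0]/n, with Satterthwaite df from the practice counts and noncentral t power. Example, 5 v 5, n = 100, ICC 0.05: variance (0.2275 + 0.1275) x 1.95/100 = 0.00692, SE 0.0832, noncentrality 0.20/0.0832 = 2.40, df 7.4, power 55%.

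| n per group | Independent patients | ICC 0.01 | ICC 0.02 | ICC 0.05 |
|---|---|---|---|---|
| 100 | 91% | 76-87% | 70-84% | 55-78% |
| 150 | 98% | 88-96% | 81-94% | 63-87% |

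Other reasonable choices of variance and df widen the n = 100 row to roughly 73-88%, 67-86% and 52-80%.

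**Planned contrast, 15% against 45%, n = 100.** The lowest power by the same t formula is 86% (5 v 5, ICC 0.05).

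**The case against.** The strongest reply is that the size of the problem is assumed throughout, and that stands. With many control practices the problem shrinks: 10 v 50 practices, n = 100, r = 0.12 gives 4.2%, 4.8% and 6.5% at the three ICCs. The one mechanism tied to individual practices concerns DCP patients. If only their outcomes are clustered (n = 100, r = 0.12), the error is 4.2-4.7%, 4.7-5.8% and 6.2-9.2%. Ignoring the pairs is conservative and offsets part of the inflation. A reader might infer that the planned test is certain to be anti-conservative. The documents do not support that: at ICC 0.01 with many practices it can sit at or below 5%.

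A reader might also fault the plan for leaving practice participation out of the propensity model. That is not an error. Participation predicts group perfectly, so it cannot serve as a matching variable. The omission that matters is in the outcome test.

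Finally, this is a nonrandomised pilot, and a clustered analysis leaves practice-level confounding in place. That lowers the priority but does not justify a test whose independence assumption the design puts in doubt.

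**Conclusion.** The concern holds in conditional form. The primary test and the stated power both assume independent patients, in a comparison where practice is nested within group, and the plan gives no values from which the effect could be bounded. Over the assumed range at 100 per group, with no within-pair correlation, the error runs from just under 6% to 16%; at 150 it reaches 21%. A within-pair correlation of 0.12 takes off about 1 to 1.5 points.

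The claim of ample power for 20 points is not assured with few practices. At 100 per group it is in doubt even at ICC 0.01-0.02. At the projected 150 it survives those ICCs with 5 or more practices per group, but is not assured at 0.05. It would go too far to infer that the study is underpowered for its main hypothesis: 15% against 45% stays well powered at 100 per group with 5 or more practices per group. The change should be made, but it is at the lower end of that category.

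**What to change.** In Statistical analysis, Aim 1, replace the simple chi-square as the primary test with one pre-specified practice-clustered analysis of the risk difference on the matched sample. Use small-sample-corrected standard errors and a t reference with df based on the number of practices. Report the 95% CI and the estimated ICC. Keep the chi-square or a McNemar test only as a sensitivity check. If too few practices contribute for clustered inference (for example one or two in a group), report the comparison as descriptive.

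In the power paragraph, state the planned number of practices per group and restate the power for this test over an assumed ICC range such as 0.01-0.05. State as a limitation that practice-level confounding remains.

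No new data collection is needed: "lists of potentially eligible individuals from participating and non-participating practices will be obtained from EMR data", and "Lists will be organized according to PCP". Practice selection is still open, so the number of practices can still be planned. The costs are wider intervals, a less favourable stated power, and an imprecise ICC estimate when practices are few. The correction is also imperfect with few uneven practices: in simulation (100 per group, 5 DCP practices, coefficient of variation of size 0.6) a leverage-corrected clustered test still rejected 6.2-7.7% under the null.

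### The primary Aim 1 test after matching is a crude, unpaired chi-square, so imbalance left in the match obtained passes into the LDCT difference; a pre-specified adjusted risk difference is a cheap improvement

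*Combined protocol and SAP*

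**What the plan says.** The Aim 1 paragraph of the Statistical analysis section states: "We will conduct a 1-to-1 propensity score matching to compare the proportion of patients who screen between the groups". The score comes from a logistic model that uses every patient-level EMR variable; participation of the practice is left out. "The nearest neighborhood method without replacement will be used for matching", and "We will set the caliper width according to the standard deviation for the propensity score", without a multiplier. The plan then adds a check: "In a second step, we will compare the characteristics of the patients and chosen controls to verify that they are very similar". It gives no numerical criterion for that check and no action if it fails.

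The only outcome analysis stated for Aim 1 is the last sentence: "We will use a simple chi-square to compare the percentage of patients in the control and intervention groups". No effect estimate, standard error, confidence interval or paired analysis is named.

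The Data Acquisition paragraph lists what the EMR holds for all patients, controls included: "gender, age, race, ethnicity, insurance status, marital status, smoking status, comorbidities" and zip code as a stand-in for socioeconomic status. The Study Design paragraph draws controls from other practices in the same health system. On size, Specific Aims plans to recruit 100. The power paragraph uses 40 and 60 per group and expects 150 to take part. No expected number of matched pairs is given.

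**The concern.** The comparison is not randomised. DCP patients have been reached and have consented, whereas controls are picked out electronically. The measured covariates are therefore the main protection. Matching on one score balances covariates on average, but not each covariate in a single small matched sample. Whatever prognostic imbalance survives the caliper and the similarity check becomes part of the observed difference in scan completion, because no later step removes it. The data needed to remove it are already held for both groups.

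The test also treats the two groups as independent samples of independent patients, although they are matched in pairs and sit within practices. At stake is the accuracy of the one estimate this pilot will produce, which the Sustainability section intends as groundwork for a randomised trial.

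**Working it through.** **1. The plan's own figure.** Inputs from the power paragraph: 15% v 45%, 40 per group. Alpha is not stated; two-sided 0.05 is assumed. Pooled SE = √(2 × 0.30 × 0.70/40) = 0.1025. Alternative SE = √((0.1275 + 0.2475)/40) = 0.0968. z = (0.30 − 1.96 × 0.1025)/0.0968 = 1.02, so power is 84.7%. The stated 85% reproduces, for an unadjusted comparison of independent groups. (The 60 per group for a 20-point difference does not: 15% v 35% gives 72.1%. That is a separate matter.)

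**2. One covariate left unbalanced.** Shift in the LDCT difference = SMD × √(prev(1 − prev)) × the covariate's risk difference, where SMD is the standardised difference. Assumed: SMD 0.1 to 0.2, prevalence 30% to 50%, risk difference 10 to 30 points.
- Low end: 0.1 × 0.458 × 10 = 0.5 points.
- High end: 0.2 × 0.5 × 30 = 3 points.

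**3. All covariates together, by simulation.** Assumed: 11 EMR-type covariates, 15 zip areas, 10 controls per DCP patient, caliper 0.2 SD of the logit, about 17% v 38%.

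| DCP patients | Covariates with SMD > 0.1 | Mean largest SMD |
|---|---|---|
| 60 | about 5 of 11 | 0.22 |
| 100 | about 3 of 11 | 0.17 |
| 150 | about 2 of 11 | 0.14 |

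In the 10% most unbalanced matches in each direction at 60, the crude difference was off by +2.4 and −2.0 points; adjusted, by 0.4 to 0.5. At 100 the two tails were about 3 points apart crude (3/2 = 1.5 each way) and near zero apart adjusted. Further runs at 60, 100 and 150 gave a gap between tails of about 2 to 5 points crude, or 1 to 2.5 each way. Adjusted, the gap was mostly within 1 point of zero, provided the adjustment list held the prognostic covariates. A setting with 30 zip codes, 15% v 35% and covariates explaining 13% of outcome variance reached about 2 points at 100 and 3 at 60.

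**4. What adjustment does not change.** In that last setting average bias was close to equal for crude and adjusted, and the variance ratio of the point estimates was 0.98 to 1.04. Power rose from 90% to 93% at 100 and from 70% to 73% at 60. A paired SE alone gave 91% and 71%, so part of the gain comes from pairing. If covariates explain only 6%, the gain is about 1 point.

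**5. Effect of ignoring the pairs.** SE = √((p₁q₁ + p₂q₂ − 2ρs₁s₂)/n), with ρ the within-pair correlation. At 15% v 35% and 100 pairs:
- ρ = 0: √(0.355/100) = 5.96 points, 95% half-width 11.7.
- ρ = 0.10: √(0.3209/100) = 5.67 points, half-width 11.1.

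The paired-to-unpaired ratio is 1.02 at ρ = −0.05, 1.00 at 0, 0.95 at 0.10 and 0.90 at 0.20. In most simulations the unpaired SE was about 0 to 6% above the true SD. In the 30-zip-code setting at 100 it was 6.2 v 5.7, or 9% above.

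**6. Effect of ignoring practices.** SE multiplier = √(1 + (m − 1) × ICC). Practice size and ICC are not in the documents. Taking m = 10 to 20 and ICC = 0.01 to 0.05 gives √1.09 = 1.04 to √1.95 = 1.40.

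Multiplying steps 5 and 6 as a rough approximation, the correct SE relative to the unpaired SE runs from 0.90 × 1.04 = 0.94 to 1.00 × 1.40 = 1.40. The range spans 1.

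**7. Type I error if only the pair is clustered.** Null simulation, 15% base rate, 100 DCP patients, 6 DCP and 20 control practices (assumed), 1,500 replicates; Monte Carlo SE √(0.05 × 0.95/1500) = 0.6 points.

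| Practice ICC | Chi-square | Adjusted, pair-clustered |
|---|---|---|
| 0 | 4.5% | 5.3% |
| 0.02 | 5.1% | 6.0% |
| 0.05 | 6.8% | 8.6% |

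**The case against.** Comparing proportions directly after propensity matching is a coherent analysis. The plan does protect balance, with all EMR variables in the score, a caliper and a post-match comparison. An error of 2 points in the worst tenth of matches is about a third of one SD (2/5.7 = 0.35) and small beside a 20 to 30 point target. At the planning effect of 15% v 45%, unadjusted power is already 95.7% at 60 and 99.8% at 100 per group; at 150 it is 98.2% even for 15% v 35%. Adjustment with pair-only clustering can also make error control worse, as step 7 shows. All of this stands. It limits the size of the point and rules out clustering on the pair alone.

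It does not remove the point. The similarity check has no stated consequence, and an adjusted estimate chosen only after the match is seen would invite selective reporting.

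Three stronger readings are tempting and are not supported:
- A reader might infer that the chi-square's error bar is too wide. The plan specifies no error bar. Ignoring pairs widens the SE only if paired outcomes correlate positively, and ignoring practices acts the other way.
- A reader might infer systematic bias from the lack of adjustment. The simulations show almost no change in average bias for the measured covariates, and adjustment cannot reach unmeasured differences between volunteers and controls.
- A reader might infer that the plan would run the same test after a failed balance check. The plan is silent on what would follow, and silence does not show that.

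**Conclusion.** The point holds as a modest one. The primary comparison uses neither the covariates, the pairs nor the practices at the outcome stage, so imbalance in the match obtained enters the LDCT difference. Its likely size is 1 to 2.5 points either way in the most unbalanced tenth of matches, and less at 150 participants. The variance error could go in either direction. The benefit of adjustment is accuracy in the particular match obtained, plus at most about 3 points of power before practice is considered.

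These sizes rest on assumed covariate strength, control pool, caliper multiplier, practice size and ICC, none of which the documents give. The gap in the analysis text itself needs no assumption.

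**What to change.** Keep the matched sample. Make the primary Aim 1 estimate a covariate-adjusted risk difference with a 95% CI, from a linear risk-difference model or a standardised logistic model. Fix about six covariates in advance from EMR fields already collected, for example age, race, insurance, marital status, COPD and area socioeconomic status.

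Use standard errors that account for practice as well as matched pairs, with a small-sample correction because practices will be few; do not cluster on the pair alone. The intervention does not vary within a practice, so practice has to enter through the variance and not as a set of fixed effects. Report the crude percentages and the chi-square as secondary. In the same edit, state the caliper multiplier and a balance threshold.

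The cost is a few sentences in the analysis section and a few lines of code, with no new data. The downside is some model dependence with few scans: at 15% v 35%, 60 pairs give 9 + 21 = 30 and 100 pairs give 15 + 35 = 50. Multi-category fields use up parameters quickly, so the list should stay short. At 60 the adjusted, pair-clustered SE was already slightly low (7.5 v a true SD of 7.7).

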Power calculation based on primary outcome: According to our preliminary study, 45% of those who complete the DCP decided to screen for lung cancer whereas the know rate of screening among patients in usual care is 15%, which makes a difference of 30%. A sample size of 40 patients in each group will achieve 85% power to detect a difference between the group proportions of 30%. The proportion in the intervention group is assumed to be 15% under the null hypothesis and 45% under the alternative hypothesis. To detect a difference of 20%, we will need a sample size of 60 patients in each group to achieve a power of 80%. We expect that 2000 patients will be identified as potentially eligible for the study in the EMR and 1000 will be reachable. Of those 300 (30%) will be confirmed eligible during the phone call and 150 (50%) will accept to participate in the DCP. We will therefore have ample power to detect a difference as small as 20% between our 2 groups.

Aim 2 Compare the characteristics of the patients not recruited in the study to the characteristics of those who accepted to enroll. *Hypothesis: Patients recruited to the study versus those who are not will be different demographically and geographically.* We will use descriptive statistics to examine the characteristics of the patients of the intervention practices who were eligible but could not be reached and of the patients who were reached but refused to be in the study. We will also compare the characteristics of these patients to those of the patients who enrolled in the study. We will use logistic regression models to determine which independent characteristics are associated with agreeing to be in the study.

Aim 3 Test the feasibility of intensive smoking cessation as part of the DCP. *This aim is hypothesis generating.* At 30 days, we will ask patients about participation in smoking cessation, quit attempts and for general comments on their needs and satisfaction with our smoking cessation efforts. We will explore trends associated with these intermediate outcomes related to cessation including engaging in cessation and quit attempts. We will illicit qualitative information from participants about how to make this part of the program useful and patient-centered.

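### The primary chi-square ignores the 1-to-1 matching, and no risk difference with a confidence interval is planned; the cost in power depends on a within-pair correlation that the plan does not give

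*Combined protocol and SAP*

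**What the plan says.** The Combined protocol and SAP, Statistical analysis, Aim 1, sets up a matched design: "We will conduct a 1-to-1 propensity score matching to compare the proportion of patients who screen between the groups". The algorithm yields disjoint pairs: "The nearest neighborhood method without replacement will be used for matching", with a caliper tied to the standard deviation of the score. The pairing is restated: "Each control will be assigned a probability score and matched with a patient in the intervention group". After a check that the matched groups look alike, the section ends with the primary test: "We will use a simple chi-square", applied to the two groups' percentages completing LDCT within 60 days.

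The section names no paired test, no variance that allows for the pairs, no reason for treating the matched groups as independent, and no risk difference or confidence interval. The power paragraph that follows is also written for two independent groups. It states no alpha, sidedness or within-pair correlation.

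**The concern.** The variance of a difference between two proportions in matched pairs has a covariance term that an independent-groups chi-square omits. If the covariates behind the propensity score also predict LDCT completion, the two members of a pair tend to have similar outcomes and the covariance is positive. The chi-square then uses too large a standard error, rejects too rarely under the null, and has less power than a test that uses the pairs.

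The missing estimate matters whatever the correlation. The Sustainability section presents this pilot as groundwork for a randomized trial. Planning that trial needs an effect size with its precision, and a chi-square p-value supplies neither.

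**Working it through.** **Inputs from the documents.** Control rate 15%, intervention rate 45%, 40 per group for 85% power; 60 per group for 80% power at a 20-point difference (all from the power paragraph). Expected size: 100 intervention patients (Specific Aims) or 150 (power paragraph).

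**Assumptions.** Two-sided alpha 0.05; 15% v 35% for the 20-point scenario; within-pair correlation phi from 0 to 0.2.

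**Step 1: reproduce the stated power.** Pooled z-test for independent proportions, n = 40, mean rate 0.30:

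- z = [0.30·√40 − 1.96·√(2·0.30·0.70)] / √(0.15·0.85 + 0.45·0.55) = (1.897 − 1.270) / 0.612 = 1.024.
- Power = Φ(1.024) = 84.7%, against the stated 85%. It reproduces, so the planned test and the power calculation agree with each other.

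**Step 2: standard error.** With s₁² = p₁(1−p₁) and s₂² = p₂(1−p₂), the ratio of the true SE to the unpaired SE is √[1 − 2·phi·s₁s₂/(s₁² + s₂²)]. At 15% v 35%: s₁² = 0.1275, s₂² = 0.2275, s₁s₂ = 0.1703.

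- phi 0: ratio 1.
- phi 0.1: √(1 − 0.0341/0.355) = 0.951; the unpaired SE is 1/0.951 − 1 = about 5% too large.
- phi 0.2: √(1 − 0.0681/0.355) = 0.899; about 11% too large.

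**Step 3: type I error.** Simulated pairs (200,000 replicates per setting), both rates 15%, joint success probability p₁p₂ + phi·s₁s₂:

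| Pairs | Test | phi 0 | phi 0.1 | phi 0.2 |
|---|---|---|---|---|
| 60 | chi-square | 4.6% | 3.7% | 2.7% |
| 60 | asymptotic McNemar | 4.7% | 4.6% | 4.4% |
| 100 | chi-square | 5.1% | 3.9% | 2.9% |
| 100 | asymptotic McNemar | 5.4% | 5.3% | 5.3% |

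**Step 4: power, chi-square v asymptotic McNemar, same simulation.**

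| Pairs and rates | phi 0 | phi 0.1 | phi 0.2 |
|---|---|---|---|
| 40, 15% v 45% | 85.2 v 84.7% | 86.3 v 87.9% | 88.1 v 91.5% |
| 60, 15% v 35% | 73.5 v 73.2% | 74.7 v 77.6% | 75.7 v 81.9% |
| 100, 15% v 35% | 91.4 v 91.1% | 92.4 v 93.7% | 93.7 v 96.2% |
| 150, 15% v 35% | 98.4 v 98.3% | 98.8 v 99.1% | 99.2 v 99.6% |

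For the 20-point difference at phi 0.2, the gap is 6.2 points at 60 pairs, 2.6 at 100 and 0.4 at 150. At phi 0 the chi-square gives up nothing. Its power rises with phi in every row, so the loss exists only relative to a paired test.

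**Step 5: which paired test.** At phi 0 with 40 pairs (15% v 45%), the exact McNemar test has 78.4% power against 85.2% for the chi-square. The exact version would therefore cost power if pairs are uncorrelated. A Wald test of the risk difference with pair-clustered errors (normal critical value, n/(n−1) correction) has a type I error of about 6% at 40 pairs.

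**The case against.** The strongest objection is that the correlation may be close to zero. Matching is on a single score, the modelled probability of being in the intervention group, so members of a pair need not resemble each other on individual covariates. They share outcome risk only so far as that score predicts LDCT completion. Under an assumed model (perfect matching on a normal score, logistic outcome, 15% v 35%), a score with AUC 0.60 for LDCT completion gives phi of 0.02, AUC 0.69 gives 0.08 and AUC 0.80 gives 0.20. A phi of 0.1 to 0.2 thus needs an AUC of about 0.72 to 0.80, which nothing in the documents supports. Pairs also share no practice, because controls come from non-participating clinics. This stands, and it is why the range starts at zero.

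Three stronger readings are tempting, and the documents do not support them:

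- **That the chi-square necessarily loses power, or that the stated power is wrong.** The loss is conditional on phi. The 85% was calculated for independent groups and still holds.
- **That the test explains the weak 20-point scenario.** At 60 per group and 15% v 35%, power is about 73% for either test at phi 0. That is a separate sample-size matter. Sixty is also a stated requirement; the plan expects 100 or 150, although caliper losses could reduce the number of pairs.
- **That the study's error rate is conservative overall.** Step 3 considers pairing alone. Intervention and control patients come from different practices, and clustering of LDCT rates by practice would push the error the other way.

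What the objection does not remove is the mismatch between a paired design and an unpaired test, or the absence of an estimate with an interval.

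**Conclusion.** The point holds in conditional form. The primary standard error ignores the pairing that the plan creates, and no risk difference with a confidence interval is planned. For phi from 0 to 0.2, the consequence is modest: at most about 11% excess in the standard error, and a pairing-only type I error between about 5% and 3%. The power forgone for a 20-point difference is at most 6 points at 60 pairs and negligible at 150.

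These sizes rest on an assumed correlation, two-sided alpha of 0.05 and a 15% base rate in the 20-point scenario. On pairing alone the error is in the cautious direction. The change is worth making because the plan states a specific rule that does not fit its design and the correction is nearly free.

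**What to change.** In Statistical analysis, Aim 1, replace the final sentence with one of two primary analyses, and state alpha and sidedness:

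- the risk difference in 60-day LDCT completion with a 95% CI and standard errors clustered on matched pair; or
- the asymptotic McNemar test, reported with the paired risk difference and its 95% CI.

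Keep the simple chi-square as descriptive. Do not specify the exact McNemar test, for the reason in Step 5 of the working. If the clustered Wald test is chosen, specify the small-sample correction, since it is slightly liberal with few pairs.

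The cost is SAP wording and slightly more analysis work on the same data. If the pairs prove uncorrelated, the asymptotic McNemar test and the chi-square give almost the same answer. Neither option deals with clustering by practice, which needs its own statement in the plan.
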